4.6.5 Disease-Specific Assessments

Except when noted otherwise (e.g., see SoA [Appendix 1](#) and below), all ocular assessments should be performed for both eyes.

The Central Reading Center will provide sites with the Central Reading Center Manual and training materials for study mandated ocular imaging. Before study images are obtained, site personnel, test images, and systems and software (where applicable) will be certified by the reading center as specified in the Central Reading Center Manual. All ocular images will be obtained only by trained and Central Reading Center-certified personnel at the study sites and forwarded to the Central Reading Center for storage and for independent analysis, including confirmation of eligibility for defined imaging criteria.

The following ocular imaging assessments will be obtained for the study eye only, except at screening where either eye has a potential to meet all eligibility criteria, and will be forwarded to the Central Reading Center:

- 7-field or wide-field color FP
- EDI SD-OCT
- 7-field FFA or wide-field FFA
- *At study visit when different imaging assessments coincide, they should be obtained on the same day.*

4.6.5.1 Ocular Safety Assessments

Ocular assessments will be performed as detailed in the SoA (see [Appendix 1](#)):

- BCVA using the ETDRS-like charts (see Section [4.6.5.2](#)); performed prior to dilating eyes
- Slit-lamp examination (scales for grading flare/cells and vitreous hemorrhage density are detailed in [Appendix 2](#))
- Dilated binocular indirect high-magnification ophthalmoscopy
- Retinal imaging: FP (including but not limited to DR severity grading), SD-OCT, and FFA. Images will be forwarded to the Central Reading Center for grading and storage.
- IOP measurement: If IOP \geq 30 mmHg at 30 (± 5) minutes post-treatment administration in the study eye, then it should be measured again at 60 (± 10) minutes post-treatment administration. The method of IOP measurement (either Goldmann tonometry or Tono-pen) used must remain the same throughout the study.
- Assessment of ocular perfusion performed as soon as possible, but not later than 15 minutes post-treatment by using finger counting, hand movement, or light perception, as appropriate

4.6.5.2 Efficacy and Pharmacodynamic Assessments

Efficacy and PD assessments will be performed as detailed in the SoA (see [Appendix 1](#)) and will include functional (BCVA), imaging assessments (FP, SD-OCT, FFA), and plasma PD biomarkers.

Additional PD sampling (e.g., where unscheduled PK sample is collected) and functional or imaging assessments can be performed at unscheduled visits at the discretion of the investigator (Section [4.6.7.5](#)).

4.6.5.2.1 Best Corrected Visual Acuity

BCVA at a starting test distance of 4 meters will be measured prior to dilating eyes by a trained and certified VA examiner masked to study drug arm assignment.

BCVA will be measured by using the set of three Precision Vision™ or Lighthouse distance acuity charts (modified ETDRS Charts 1, 2, and R). A VA Manual will be provided to the investigators. VA examiner and VA examination room certifications will be obtained before any VA examinations are performed.

The BCVA examiner will be masked to study eye and treatment assignment and will only perform the refraction and BCVA assessment (e.g. Visual Acuity Specification Manual). The BCVA examiner will also be masked to the BCVA letter scores of a patient's previous visits and may only know the patient's refraction data from previous visits. The BCVA examiner is not allowed to perform any other tasks involving direct patient care.

4.6.5.2.2 Fundus Photography

Seven-field or wide-field FP will be performed at the study sites by trained and Central Reading Center-certified personnel. Where both 7-field and wide-field devices are available, wide-field FP should be performed. It is mandatory that the same device is used for the entire duration of the study.

FP images might include red-free, color, and infra-red, as further specified in the Central Reading Center Manual.

4.6.5.2.3 Enhanced Depth Imaging Spectral Domain Optical Coherence Tomography

Enhanced Depth Imaging SD-OCT will be performed at the study sites by trained and Central Reading Center-certified personnel on a Spectralis instrument (Heidelberg Engineering, Heidelberg, Germany), equipped with TrueTrack Active Eye Tracking, AutoRescan, and EDI. Where Spectralis is not available at an investigational site, Cirrus, Topcon, or Optovue are acceptable devices. It is mandatory that the same device is used for the entire duration of the study.

Images should be acquired and transferred to the Central Reading Center according to specifications provided in the separate Central Reading Center Manual.

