1.2.2.3 Functional and Anatomical Pharmacodynamics

Higher BCVA was observed in patients treated with RO6867461 compared to baseline in the Phase I study. In the SAD part, a median 7 letter (range: 0 to 18; n=11) higher BCVA was observed on Day 28 as compared to baseline across all patients. In the MAD part, after the first, second, and third administration of 6 mg RO6867461, a median BCVA increase from baseline of -0.5, 3, and 7.5 letters, respectively, was observed, while no change in BCVA was seen with the 3 mg RO6867461.

The changes in BCVA were associated with a reduction in central subfield thickness (CST). A median change from baseline of -42 μ m in CST on Day 28 pooled for all dose levels was observed in Part A. For the patients treated with 3 mg RO6867461 in Part B, a median change from baseline of -13.5 μ m, -25.0 μ m, and -9.0 μ m at 28 days after the first, second, and third drug administration, respectively, was observed. Patients in the 6 mg RO6867461 in Part B showed a consistent and durable reduction in CST, with an overall magnitude comparable to Part A. The CST median change from baseline was -79.5 μ m, -86 μ m, and -117 μ m at 28 days after the first, second, and third drug administration, respectively. There was no overall apparent change in the fundus fluorescein angiography (FFA).

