3.1.2 Number of Patients

Up to 210 patients will be randomized. Approximately 150 treatment-naïve patients and approximately 60 patients who have been previously treated with IVT anti-VEGF will be enrolled in the study. Approximately 50 treatment-naïve patients will be randomized

RO6867461—F. Hoffmann-La Roche Ltd
28/Protocol BP30099, Version 3

into each arm (1:1:1 randomization scheme) and approximately 30 patients previously treated with IVT anti-VEGF will be randomized into arms A and C.

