4.3 METHOD OF TREATMENT ASSIGNMENT AND MASKING

4.3.1 Treatment Assignment

After written informed consent has been obtained, all patients will receive a screening number assigned through the interactive voice and web response system (IxRS).

A patient must satisfy all eligibility criteria (see Section 4.2.1 and Section 4.2.2) at the screening or Day 1 visit (as defined for each individual criterion in Section 4.2 and below) prior to randomization and first study treatment (see Section 4.6.7.1). As part of the screening process, FP, FFA, and SD-OCT will be transferred to the central reading center, and a set of images will be evaluated to provide an objective, masked assessment of certain eligibility criteria.

Only one eye will be selected as the study eye. See Section 4.6.7.1 for details.

After all patient eligibility requirements are confirmed on Day 1 visit (see Section 4.2), including:

- Baseline BCVA letter score of 73 to 24 letters (inclusive) in the study eye
- Absence of active intraocular inflammation in the study eye
- Absence of febrile illness within one week prior to Day 1,

the site personnel will contact the IxRS for assignment of a patient identification number (a separate number from the screening number).

Treatment naïve patients will be randomized in a 1:1:1 ratio to one of the arms A, B and C, respectively. Patients previously treated with IVT anti-VEGF will be randomized in a 1:1 ratio to arms A and C.:

- Arm A: 0.3 mg ranibizumab IVT
- Arm B: 1.5 mg RO6867461 IVT

RO6867461—F. Hoffmann-La Roche Ltd
37/Protocol BP30099, Version 3

- Arm C: 6 mg RO6867461 IVT

This study will consist of a treatment period (20 weeks) and an observational period (up to 16 weeks), for a total study length of up to 36 weeks. During the treatment period, the study drug will be administered to the patients on Day 1 and on every 4th week, for a total of 6 injections. During the observational period, patients will be evaluated every 4th week. If during any of these evaluations the patients meet the pre-specified criteria (see Section 4.3.1.1), the patients will receive a single dose of 0.3 mg ranibizumab and exit the study. They will receive a follow up phone call 7 days after the dose of ranibizumab to evaluate any potential adverse events. Otherwise, patients will exit the study once they have completed the observational visit at week 36.

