6. STATISTICAL CONSIDERATIONS AND ANALYSIS PLAN

6.1 DETERMINATION OF SAMPLE SIZE

The sample size is based on the primary efficacy outcome of mean change in BCVA from baseline at Week 24 in the *treatment-naïve patients*. Each RO6867461 dose (Arms B and C) will be compared with the control group (Arm A).

Consider 50 *treatment-naïve* patients randomized to Arms A, B, and C, with a drop-out rate of 10%. Assuming a standard deviation of 11 letters, this sample size provides 80% power to detect a true difference of 5 letters at the one-sided α level of 10%. The minimum detectable difference is approximately 3 letters.

Approximately 60 previously IVT anti-VEGF treated patients will be enrolled in addition for exploratory analyses.

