The primary efficacy variable is the study eye BCVA change from baseline at Week 24. The primary efficacy analysis will be performed using a Linear Mixed Effects Model for Repeated Measurements (MMRM) model. The model will include the categorical covariates of treatment group, categorical visit, and visit by treatment group interaction term, randomization stratification factors, and a continuous covariate of baseline BCVA. An unstructured covariance will be used to account for within-patient correlation (General Linear Model), but another variance-covariance structure such as AR(1) + random patient effect may be selected in case of convergence issues. The primary statistical test will aim to test the null hypothesis:

H_0 : There is no difference between either of the RO6867461 arms (Arms B and C) and the control group (Arm A) for mean BCVA change from baseline at Week 24 in the treatment-naïve patient population vs.

H_A : Arm B or C is different from arm A.

The model-based estimate of the difference between each of the treatment groups (Arms B and C) and the control group (Arm A) at Week 24, together with 80% confidence interval and corresponding p-value will be reported as the primary

efficacy measures. The mean and 80% CI within each treatment group and for the difference between RO6867461 treatment groups (Arms B and C) and the control group (Arm A) at the other time points will also be reported. There will be no formal correction for multiple comparisons. Tests for arms B vs A and C vs A will be carried out at one-sided 10% alpha.

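### The primary BCVA model leaves out baseline central subfield thickness, a planned pre-dose measurement for every randomised study eye; adding it could give a modest precision gain of unknown size

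*Protocol*

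**What the plan says.** **Model.** Protocol 6.7.1 specifies an MMRM with treatment, visit, their interaction and baseline BCVA. SAP 3.5.1 keeps these terms and ends its covariate list with "randomization stratification factors, and a continuous covariate of baseline BCVA". The stratification factors are BCVA category, previous macular laser and previous intravitreal anti-VEGF (Protocol 4.3.1, SAP 2.1). Edema severity therefore enters neither the model nor the stratification.

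**Measurement.** The Schedule of Assessments (Protocol Appendix 1) marks SD-OCT on Day 1 as a baseline assessment, and imaging after screening is of the study eye only. Protocol 4.6.5.2.3 says "Enhanced Depth Imaging SD-OCT will be performed at the study sites by trained and Central Reading Center-certified personnel on a Spectralis instrument" and accepts Cirrus, Topcon or Optovue where a site lacks that device, with one device kept for the whole study. Images go to the Central Reading Center for grading (Protocol 4.6.5.1), and SAP Table 1 names the reading-center variable for mean CST. Entry thresholds differ by device: 325 µm for Spectralis, 315 µm for Cirrus and Topcon, 295 µm for Optovue (Protocol 4.2.1). Baseline is the last non-missing value before the first dose (Protocol 6.4, SAP 3.4.2).

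**Other covariates.** Protocol 6.7.2 allows baseline parameters as covariates. SAP 3.5.2 goes further and commits to evaluating their influence on the primary endpoint, with a pointer to a section 4.4.5 that the SAP's numbering does not contain. Neither passage names CST or places it in the primary model.

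**The concern.** Adjusting a continuous outcome for a prognostic baseline variable shortens the interval for each dose-versus-ranibizumab contrast and removes the effect of chance imbalance in that variable. CST is a reasonable candidate. Patients enter on macular thickening, their vision loss must be attributable mainly to DME, and eyes whose vision would not recover when edema resolves are excluded. The value is already planned, so using it needs no extra patients or visits.

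With about 50 treatment-naïve patients per arm, and an interim look at about 28 per arm that informs development options, a chance difference in baseline edema could move the observed contrast by a noticeable part of a letter. Naming the covariate in advance also avoids choosing it after results are seen.

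**Working it through.** **Inputs.** "Assuming a standard deviation of 11 letters" (Protocol 6.1). "Approximately 50 treatment-naïve patients will be randomized" to each arm (Protocol 3.1.2), less 10% drop-out: 50 × 0.9 = 45 evaluable per arm, 135 in all. "Treatment naïve patients will be randomized in a 1:1:1 ratio to one of the arms A, B and C, respectively" (Protocol 4.3.1), so each contrast is 1:1. "Tests for arms B vs A and C vs A will be carried out at one-sided 10% alpha" (SAP 3.5.1), so z = 1.2816. The partial correlation r of baseline CST with Week 24 BCVA change, given the covariates already in the model, is **not in the documents**; it is assumed and shown as a range.

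**Step 1: reproduce the plan.** Protocol 6.1 claims "80% power to detect a true difference of 5 letters at the one-sided α level of 10"%.
- SE = 11 × √(2/45) = 2.319 letters.
- Power = Φ(5/2.319 − 1.2816) = 80.9%.
- Minimum detectable difference = 1.2816 × 2.319 = 2.97 letters, against about 3 stated.

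The plan's figures hold without CST.

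**Step 2: add baseline CST.** SE = 2.319 × √(1 − r²); power = Φ(5/SE − 1.2816); equivalent evaluable number per arm = 45/(1 − r²).

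| Assumed r | SE (letters) | 80% CI half-width | Power | Equivalent n per arm |
|---|---|---|---|---|
| 0 | 2.319 | 2.97 | 80.9% | 45.0 |
| 0.1 | 2.307 | 2.96 | 81.2% | 45.5 |
| 0.2 | 2.272 | 2.91 | 82.1% | 46.9 |
| 0.3 | 2.212 | 2.84 | 83.6% | 49.5 |

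**Step 3: charge for the parameter.** Take a single-visit approximation with six parameters already fitted: intercept, two treatment terms, baseline BCVA and two strata (previous anti-VEGF is constant in treatment-naïve patients). One more term inflates variance by about 1/(135 − 6 − 2) = 1/127 = 0.8%. The net variance factor is (1 − r²) × 1.0079:
- r = 0.1: 0.998, power 81.0%
- r = 0.2: 0.968, power 81.9%
- r = 0.3: 0.917, power 83.4%

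Break-even is r = √(1 − 1/1.0079), about 0.09. If CST were entered with a four-level device factor (four extra terms) and device itself had no prognostic value, the cost would be about 4/127 = 3.1%. Break-even would then be about r = 0.17, and r = 0.1 would be a net loss.

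**Step 4: chance imbalance.** A one-standard-error imbalance in baseline CST is √(2/45) = 0.21 SD. Unadjusted, it shifts the contrast by r × 11 × 0.21, which is 0.46 letters at r = 0.2 and 0.70 at r = 0.3. At the 28-per-arm interim, √(2/28) = 0.27 SD gives 0.59 and 0.88 letters.

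**Limits.** The documents do not say whether the SD of 11 is raw or already adjusted for baseline BCVA; the proportional effect on SE is the same either way.

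**The case against.** The strongest objection is that nothing in the plan is wrong. Power is met, omitting a covariate does not bias a randomised comparison, and the benefit rests wholly on an assumed correlation. That stands, and it sets the weight of the point. Even at r = 0.3 the 80% interval half-width shrinks only from 2.97 to 2.84 letters.

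Three stronger readings are tempting, and the documents do not support them.

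- *That the protocol shows CST to be prognostic.* Protocol 1.2.2.3 reports "The changes in BCVA were associated with a reduction in central subfield thickness (CST". That concerns change in CST after treatment, not baseline CST, in a small Phase I study of previously treated AMD patients. The two measures also tracked loosely there: after the first 6 mg dose in the multiple-dose part, median CST fell 79.5 µm while median BCVA changed by −0.5 letters. Use as an entry criterion is not evidence of prognostic value either.
- *That the SAP rules CST out because its sensitivity analysis lists only age.* The list in SAP 3.5.4 stops at a page break after one item, so it cannot show what is absent. SAP 3.5.2 leaves room for a CST-adjusted analysis.
- *That the precision is free.* Four devices are allowed and scans may be ungradable, so rules are needed. The entry thresholds are given as eligibility cut-offs; nothing says that they equal the devices' measurement offsets.

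What survives is narrower: CST is planned for every randomised study eye, is plausibly prognostic, and is not prespecified in the primary model.

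**Conclusion.** The point holds as an optional improvement. Both versions of the primary model omit a planned, centrally graded pre-dose measurement. A reader might infer that the primary analysis is biased or underpowered; neither follows, since randomisation protects the comparison and 80.9% power is reached without CST.

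For assumed partial correlations of 0.1 to 0.3 the gain is 0.3 to 2.7 percentage points of power, or about 0.1 to 2.5 points after the cost of one parameter. It is nil below about r = 0.09. The figures assume an SD of 11, 45 evaluable patients per arm, and a CST effect at Week 24 that the model captures fully. Protection against chance imbalance in edema severity is a further benefit, worth up to about 0.7 letters for a one-standard-error imbalance at r = 0.3. The true r is unknown from these documents.

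**What to change.** Before any unmasked analysis, including the 28-per-arm interim, amend SAP 3.5.1 as follows.

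1. Add baseline CST of the study eye as a continuous covariate in the primary MMRM.
2. Centre it within device, or on the device's entry threshold, in preference to a four-level device factor. Within-device centring does not rely on the thresholds being true measurement offsets.
3. Use the latest gradable pre-dose scan, taking the screening scan if Day 1 is missing. If neither is usable, apply a simple baseline imputation that ignores treatment arm, so that no patient drops out of the primary model.
4. Keep the current model as a sensitivity analysis.

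The cost is one degree of freedom, about 0.8% of variance if CST proves uninformative, plus short device and missing-scan rules. No new data, visits or patients are needed.

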4.6.5.2.4 Fundus Fluorescein Angiography

Seven-field FFA (30 degree field of view) or wide-field FFA (e.g., Optos, Spectralis) will be performed at all the study sites by trained and Central Reading Center-certified personnel. Where both devices are available, wide-field FFA should be performed. It is mandatory that the same device is used for the entire duration of the study.

Images should be acquired and transferred to the Central Reading Center according to specifications provided in the Central Reading Center Manual.

4.6.5.2.5 Plasma Pharmacodynamic Biomarkers

Samples for plasma PD biomarkers will be taken at the time-points detailed in the SoA (see [Appendix 1](#)). The following analyses will be performed:

- Change from baseline in plasma levels of VEGF and Ang-2

Any residual material from PD biomarker samples may be used for additional exploratory biomarker profiling, identification, assay development purposes, and assay validation during the development of the study or compound-related assays, after the mentioned intended uses. All samples will be destroyed up to 2 years after the final closure of the database and all intended data have been verified.

4.6.6 Amount of Blood to be Collected throughout the Study

Throughout the study, a total of approximately 185 mL of blood will be drawn from each patient, to perform clinical laboratory assessments, determine plasma concentrations and perform genetic and PD/exploratory assessments.

4.6.7 Timing of Study Assessments

4.6.7.1 Screening and Pretreatment Assessments

Written informed consent for participation in the study must be obtained before performing any study-specific screening tests or evaluations. Informed Consent Forms for enrolled patient and for patients who are not subsequently enrolled will be maintained at the study site.

All screening and pretreatment assessments must be completed and reviewed to confirm that patients meet all eligibility criteria, including Central Reading Center confirmation of eligibility for a predefined set of imaging criteria, and defined list of Day 1 assessments (see below). The investigator will maintain a screening log to record details of all patients screened and to confirm eligibility or record reasons for screening failure.

Only one eye will be selected as the study eye. Where both eyes meet all eligibility criteria, the eye with worse BCVA will be defined as the study eye. Where both eyes meet all eligibility criteria and have the same BCVA letter score at Day 1, study eye selection is at the investigator's discretion.

An Eligibility Screening Form (ESF) documenting the investigator's assessment of each screened patient with regard to the protocol's inclusion and exclusion criteria is to be completed by the investigator and kept at the investigational site.

Patients who are willing to participate in the study and have given informed consent will undergo a thorough screening examination within 4 weeks before study drug administration. The list of screening procedures is outlined in the SoA (see [Appendix 1](#))

After the screening visit, ocular images of both eyes will be forwarded as soon as possible to the Central Reading Center for those patients who meet all non-ocular eligibility criteria (eligibility for safety labs, ECG, and pregnancy test, where appropriate, might be pending). The Central Reading Center will assess the image data submitted and confirm eligibility for study eye imaging criteria. Confirmation of eligibility by the Central Reading Center for the study eye imaging criteria is required.

On Day 1 prior to enrollment, all patient eligibility requirements are reviewed, and relevant eligibility criteria (Section [4.2](#)) are confirmed, including but not limited to the following criteria:

- Baseline BCVA letter score of 73 to 24 letters (inclusive) in the study eye

RO6867461—F. Hoffmann-La Roche Ltd
57/Protocol BP30099, Version 3

- Absence of active intraocular inflammation in the study eye
- Absence of febrile illness within one week prior to Day 1,

Patients will be enrolled if they meet all screening and Day 1 eligibility criteria.

Where febrile illness is identified within 6 days of the scheduled Day 1 visit, or on the date of the visit, the Day 1 visit must be rescheduled at the earliest 7 days after the end of the febrile illness episode and no later than 4 weeks after the screening visit.

Patients who failed screening due to:

- *febrile illness (where "end of febrile illness + 7 Days" extends beyond the 4 week screening period)*
- uncontrolled blood pressure
- *administrative reasons (e.g. unable to schedule Day 1 within 28 days from the screening visit)*
- *not meeting eligibility criteria for the study eye: in the event the patient might be eligible to participate for the second eye after the initial screening period.*

will be allowed to be re-screened. If patients meet criteria upon re-screening, they will receive a new screening number and will be treated as a new patient.

For each patient, if one eye does not meet eligibility criteria, then the second eye may be evaluated within the initial screening period. If the second eye meets the eligibility criteria, then the patient would retain the same screening number and would not be screened-failed.

